3. BACKGROUND

Rationale & Supporting Data:

Cerebral vasospasm is a devastating health problem that is a major contributor to poor outcome following subarachnoid hemorrhage (SAH). The estimated case fatality following a SAH is 25-50% with a large proportion of these being secondary to the deleterious consequences of delayed cerebral vasospasm^{1, 2}. Up to 70% of patients who survive the initial SAH develop signs of vasospasm, which, if untreated, can lead to devastating strokes ^{1,3,4}. To this date, the armamentarium available for predicting, preventing, and optimizing outcomes following severe vasospasm remains limited.

The reason for this poor result is, in part, that the complex pathogenesis of vasospasm has not been completely explicated. What is clear though is that between 3 and 21 days after SAH, severe vasoconstriction of the intracranial arteries frequently occurs, leading to delayed ischemia and commonly devastating strokes.

Despite improved microsurgical and endovascular techniques used to treat aneurysms, we have not made significant strides in treating cerebral vasospasm. The traditional therapy acutely using hypertensive hypervolemic hemodilution, which has been adopted in clinical practice, presents considerable cardiopulmonary risks. Endovascular treatments such as angioplasty and intra-arterial drug delivery, particularly of calcium channel blockers, have been considered the quintessential treatment for minimizing potential devastating ischemic stroke resulting from delayed cerebral vasospasm.

Based on the results of a recent national survey conducted by the two PI's of this study through the joint AANS/CNS cerebrovascular section, there is considerable variability in how intra-arterial of cerebral vasospasm is treated. This has led to variable outcomes.

The commonly used intra-arterial drugs for treating vasospasm are used as single agents, among them being verapamil⁵, nicardipine^{6, 7} and nitroglycerin. The clinical result is generally considered unsatisfactory. There has been no literature that conclusively recommends an optimal intra-arterial infusion agent or combination of agents for treating cerebral vasospasm, particularly when balloon angioplasty is not feasible for the involved arteries. The end result of treatment is thus generally unsatisfactory.

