4. STUDY DESIGN

This is a prospective multicenter randomized controlled clinical trial. Endovascular treatment will be initiated on hospitalized patients who present with cerebral vasospasm within 3-21 days following surgical or endovascular intervention for aneurysmal subarachnoid hemorrhage (aSAH). Endovascular treatment will consist of:

- 1. Diagnostic angiogram to locate the spasmic blood vessel/vessels.
- 2. Pharmacological cerebral angioplasty to treat presenting spasm in one or two the following arterial vessel territories (if all three territories need treatment: the patient is excluded from participation in the study)
 - a. Right Carotid Artery Territory: to treat Vasospasm in R Carotid, R ACA, R MCA & its branches
 - b. Left Carotid Artery Territory: to treat Vasospasm in L Carotid, L ACA, L MCA & its branches
 - c. Vertebral-Basilar Territory
- 3. Post-treatment angiogram.
- 4. Balloon angioplasty may be done if vasodilators fail to produce response or show insufficient improvement.

Please refer to Appendix IV Study flow chart for the detailed study design & Flow

Randomization:

Study participants will be randomly assigned to one of three treatment groups. Randomization will be pre-determined and specific to each participating center. At each center only the Research Coordinator/Nurse will have access to the randomization pattern.

Treating physicians will not be blinded by the randomization scheme and will know the drug group assigned to the study subject *only after the first diagnostic angiogram has been performed, when he/she confirms the need for drug treatment.*

However, the subjects enrolled in the trial will be blinded and will not know the treatment group to which they have been assigned.

TREATMENT CRITERIA

- 1. Symptomatic vasospasm clinical symptoms, with or without Trans-cranial Doppler (TCD) study.
- 2. 50% or more stenosis seen on diagnostic angiogram in asymptomatic patients

DRUG DOSE: Patients who qualify for endovascular treatment post aSAH will be randomly assigned to one of three treatment groups:

Group 1: Nicardipine (Cardene): 5 mg per circulation in 25 mL 5% Dextrose. Infusion rate: 1.25 mL/minute over a period of 20 minutes

Group 2: Verapamil: 10 mg per circulation in 10 ml saline. Infusion rate: 1 mL/minute over a period of 10 minutes.

Group 3:

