- The length of time from aneurysm rupture to time of surgical intervention
- Time in between vasodilator applications
- Number of drug applications used
- Dose of drug applications
- Pre- and post-procedure intracranial pressure measurements (ICPs)
- Cardiovascular instability (SBP changes in mm Hg, requirement of intravenous [IV] pressors)
- New strokes on CT
- Modified Rankin Scale, NIHSS (before treatment, at discharge, and at 3 months after discharge)

Patients will have a 3-month follow-up clinic visit as per standard of care after discharge from the hospital.

5. SELECTION AND ENROLLMENT OF SUBJECTS

Inclusion Criteria: Only adult patients ≥ 18 years with ruptured aneurysms requiring surgery or endovascular therapy and who experience vasospasm post-operatively (3-21 days post-procedure) will be enrolled in this study.

Informed consent will be obtained either from the patient or the patient's legal representative. The institutional PI/Co-PI will determine the **eligibility of the patients** for the study on the basis of the following:

- Adult patient, age 18 80 years old, with ruptured aneurysm(s) who experience vasospasm postoperatively within 3-21 days.
- Symptomatic vasospasm (clinical or TCD)
- For centers that perform a routine day 7 angiogram post-aneurysm treatment 50% or more stenosis seen on diagnostic angiogram for asymptomatic patients.

Exclusion Criteria:

- Inability to obtain consent from patient or patient's family
- Pregnant women (confirmed by a positive pregnancy test)
- Hunt Hess (HH) grade 5
- Intra-arterial drug treatment in all 3 arterial territories

Study Centers:

The University of Texas Medical School at Houston University of Illinois College of Medicine – Chicago Geisinger Health System, North Shore University Hospital – Northwell Health

Study Enrollment Procedures:

Institutional PI & Co-PI will determine a patient's eligibility based on SOC testing and procedures used in treating patients with aneurysms.

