7. CLINICAL AND LABORATORY EVALUATIONS

For this clinical trial no additional clinical or laboratory evaluations are required apart from the standard hospital routine care procedures. The required evaluations are listed below: Schedule of Evaluations

Table 1.			-	
Evaluation	Screening	Pre-	Post –	3 months
	_	Vasospasm	Vasospasm	Follow up
		Treatment	Treatment	1
Informed Consent	Y			
Pregnancy Test	Y			
Clinical examination mRS, NIHSS, (24-hr window)	Y	Y	Y	Y
NON-contrast CT scan (24-hr window)	Y	Y	Y	Y
TCD (Lindegaard Index)	Y	Y	Y	
Pharmacological angioplasty	Intervention			

Balloon angioplasty	Concomitant intervention			
Intracranial pressure	Y Y		Y	
Enter Clinical DATA in REDCAP	ENTER within 1 week of discharge & F/U			

Time Frame:

Pre-vasospasm treatment: 24 hours prior to procedure

Post-vasospasm treatment: within 24 hours of the procedure

3-month follow-up visit: +/- 2 weeks

Core Lab Image upload: Please upload all angiogram and CT scan images of the patients enrolled each month to the core lab website by the 7th calendar day of the preceding month.

Evaluations:

Screening & Pre-entry: Screening & pre-entry evaluations may occur simultaneously. Any patient who presents with cerebral vasospasm within 3-21 days after aneurysmal SAH and has an intervention done for aneurysm rupture is eligible for this clinical trial assuming other inclusion criteria are met.

Entry: On confirming patient eligibility and informed consent process, the patient will be randomly assigned to one of the three treatment groups for intra-arterial infusion of study drugs.

On-Study/On-Intervention Evaluations: Pharmacological angioplasty

Intervention Discontinuation Evaluations: If for any reason the PI or the Co-PI discontinue the intervention on a patient, the data will still be collected and entered into the data sheet; patients will still receive all medical & surgical care they need as per routine hospital care procedures. During analysis data from discontinued participants will be factored in.

- On Study/Off-Intervention Evaluations: Before discharge from hospital after intervention, patient's neurological status will be noted using Modified Rankin scale and NIH Stroke Scale [NIHSS]. Any new changes on CT scan should be noted, ICP should be noted, and any procedure complications or delayed procedure complications should be noted.

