In order to ensure patient safety and integrity of data collection, data and safety monitoring during this trial will include both internal and external mechanisms. The PI has developed an internal monitoring system, which will be implemented after each enrolled patient and on a monthly basis at the host site, University of Texas Health Science Center Houston. The study team will perform internal monitoring. In addition, on a yearly basis, a monitor will be asked to review study and safety data for all participating centers. Monitoring of participating centers will occur on a yearly basis, or following the completion of the study for each additional two subjects at each center, whichever occurs first. Monitoring may occur in person, or remote. Lastly, the Data and Safety Monitoring Board will independently review the accumulating data, assess the risk to benefit ratio, and can consider halting the trial if the risk to benefit ratio is deemed unacceptable. The external monitor and the DSMB will also monitor protocol compliance, safety, and onschedule study progress.

11. DATA COLLECTION, SITE MONITORING AND ADVERSE EVENT REPORTING

Data collection: detailed clinical information will be gathered using an established method approved by UT Health for abstracting information from electronic database and by the approved established method at each participating site.

Each participating center will use REDCap data software an online secure web application to enter the data in the central REDCap database managed by UT-Houston.

All the radiographic images will be evaluated and analyzed by a single CORE LAB (at The University of California – Los Angeles) centrally in blind fashion. The radiographic images will be submitted via VPN with security and with federal Health Insurance Portability and Accountability Act (HIPPA) compliance.

The patient's demographics (gender, age, race, BMI, co-morbidity, tobacco use, cocaine/illicit drug use history), aneurysm treatment modality, days after the SAH and aneurysm treatment, vasodilator(s) used (Group #) and numbers of the treatment sessions will be submitted via REDCap. Summaries will be provided quarterly to the DSMB members.

Records to Be Kept: All patient data will be de-identified and CRFs will be stored on password protected cloud drive

Data and Safety Monitoring Plan & Quality Assurance:

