Serious adverse event	 Any AE that a) led to death, b) led to serious deterioration in the health of the subject that either resulted in 1) a life-threatening illness or injury, or 2) a permanent impairment of a body structure or a body function, or 3) in-patient or prolonged hospitalization, or 4) medical or surgical intervention to prevent life-threatening illness or injury or permanent impairment to a body structure or a body function, NOTE: Planned hospitalization for a pre-existing condition, or a procedure required by this Protocol, without serious deterioration in health, is not considered a serious adverse event. (ISO 14155, 2011)
Technical Event	A study procedure related event.
Stroke	New Stroke event, worsening of motor, sensory or speech function. Cant be explained by cerebral vasospasm and or pre-existing aSAH Clinically and radiographically.
Neurologic Death	For the purposes of study endpoints, neurologic death is defined as any death determined to be of neurologic cause. This definition excludes: death due to rupture of a nonindex aneurysm or as a consequence of treatment of a nonindex aneurysm.
Death	For the purposes of study endpoints, death excludes death of accidental causes or death due to rupture of a nonindex aneurysm or as a consequence of treatment of a nonindex aneurysm.

Study procedure related Minor complications might include:

Nausea and/or vomiting (post-anesthesia) Mild headache Groin discomfort: mild pain and or bruising at the incision site

Study Procedure related **Significant complications** (catheter induced: different from preexisting cerebral vasospasm & SAH induced ischemia): Intra-cranial catheter induced spasm of the treated segment of artery or branches Stroke (ischemic, hemorrhagic, TIA) Hemiplegia Aphasia Visual impairment or blindness Intra cranial artery tear (hemorrhage) Femoral artery occlusion due to catheter

Study Procedure related Very Rare side effects may include: Death Renal failure due to dye induced Seizure Infection Blood vessel or nerve damage Decreased blood flow in the leg on the side of the groin puncture A pseudoaneurysm may develop as a result of injury to all the layers of a vessel wall resulting in a hematoma Air embolism Mental status changes Total occlusion of the treated blood vessel segment or other blood vessels.

DRUG RELATED adverse events & overdose effects:

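### The Stroke definition leaves out events that vasospasm or the aSAH can explain, so new infarcts can fall outside that category and outside the relatedness filters, and new strokes on CT have no planned analysis

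*Combined protocol and SAP*

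**What the plan says.** - **Definition (Appendix III, Stroke).** The event is a "New Stroke event, worsening of motor, sensory or speech function", with the condition that it "Cant be explained by cerebral vasospasm and or pre-existing aSAH Clinically and radiographically".
- **Procedure complications (Appendix III).** The list of significant complications, which includes stroke, carries a similar limit: "catheter induced: different from preexisting cerebral vasospasm & SAH induced ischemia".
- **48-hour report (section 8).** It covers events that are at once serious, unanticipated and related, plus unanticipated problems involving risk.
- **DSMB adjudication (end of Appendix III).** The board reviews serious related AEs, with new ischaemic stroke among the examples, and classes them as due to procedure, drug or other cause.
- **General AE and SAE definitions (Appendix III).** Neither has a vasospasm exclusion, and an AE counts whether or not a study drug caused it.
- **CT data.** Section 4 lists "New strokes on CT" among the data collected. Section 7 adds, for the period before discharge, "Any new changes on CT scan should be noted".
- **Analysis (section 10).** The secondary outcomes are mRS, SAE occurrences and treatment failure with balloon angioplasty. Stroke and new CT infarct are not among them.
- **Blinding.** Section 4: "Treating physicians will not be blinded by the randomization scheme". Section 11: "All the radiographic images will be evaluated and analyzed by a single CORE LAB", in blinded fashion. Section 7 has the sites upload CT scans as well as angiograms.

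**The concern.** Section 3 describes severe vasoconstriction after SAH as "leading to delayed ischemia and commonly devastating strokes", and presents endovascular treatment as the means of limiting such strokes. An infarct after a regimen has failed to open the vessel is therefore a clinical failure that this trial should be able to show by arm. The definition sets that event aside, because vasospasm explains it.

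A second kind of event is less clear. Appendix II reports hypotension with intra-arterial nicardipine, and Group 3 receives the per-circulation dose of each single agent plus nitroglycerin, so vasodilator load differs by arm. If pressure falls and a territory already in spasm infarcts, the cause is mixed. The definition does not say how to class it.

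At stake is whether the DSMB and the final report can see new strokes by arm, or only those that someone has judged not to be due to the disease.

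**Working it through.** The documents give no stroke rate, stroke sample size or stroke power, so there is no figure to reproduce. The check is to follow events through the text.

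**1. To whom does the exclusion apply?** Section 5 requires vasospasm 3 to 21 days after the aneurysm procedure. All subjects, up to 330, therefore have the condition that the definition accepts as an alternative explanation.

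**2. Where does each kind of infarct go?**

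| Event | Stroke category | Routes limited to related events | SAE tally | CT item |
|---|---|---|---|---|
| Catheter-induced, not explained by spasm | Yes | DSMB list if serious; 48-hour report if also unanticipated | If serious | Yes, if seen |
| In a vessel the regimen failed to open | No, read as written | Can be missed if judged disease-related | If serious | Yes, if seen |
| Mixed cause, e.g. pressure drop in a spastic territory | Undetermined | Undetermined | If serious | Yes, if seen |
| On CT with no new deficit | Unclear, since the wording stresses function | Depends on seriousness and attribution | Only if a seriousness criterion is met | Yes |

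The first two columns depend on attribution. The last two do not.

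**3. What is done with the last two columns?** Section 10 summarises SAE occurrences as one outcome, so a difference in stroke is mixed with every other serious event. It assigns no table or test to the CT item.

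**4. Who attributes cause, and when?** Nobody is named to apply the exclusion. The definition gives no starting point, such as the first study infusion, and no rule for mixed causes. The DSMB adjudicates cause only for events that have already passed as serious and related. The core lab receives the CTs, but the reading task spelled out in section 4 is vessel diameter. No text gives it stroke attribution or infarct reading as a task.

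**The case against.** The strongest reply is that these events remain visible elsewhere.

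- The SAE outcome has no cause filter. Section 8 also has a five-day notice of serious adverse events that is not limited to related ones. This stands: serious infarcts do not leave the safety data. But the SAE outcome is pooled and does not show stroke by arm.
- Failure to open the vessel is lack of efficacy, which PIIR, balloon-angioplasty failure and 3-month mRS address. This stands in part. None of the three counts infarcts.
- Separating disease events from treatment complications is a recognised choice. It is, but it can be made by classifying events after they are counted.
- The DSMB has a general remit in section 10 to review accumulating data, and hemiplegia, aphasia and visual impairment have their own entries in its list. Both are true. Those entries still sit under the heading of related events, so the relatedness filter matters there as much as the definition.
- The final words of the definition may mean that both clinical and radiographic grounds are needed before an event is set aside. That would narrow the exclusion; the text does not settle it.

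A reader might also infer that an unblinded treating team decides which strokes count. Treating physicians do know the assigned drug, but no text gives them this decision. What the documents support is that no adjudicator, blinded or otherwise, is named.

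**Conclusion.** The point holds as a gap in safety reporting. Read as written, the definition lets infarcts after failed treatment fall outside Stroke and outside the routes restricted to related events. Infarcts of mixed cause may follow them. That second part is an inference: Appendix II names hypotension as a nicardipine effect, reports little haemodynamic effect for the other two drugs, and does not link hypotension to infarction.

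The size cannot be stated, because the documents give no stroke rate and no indication of how often vasospasm would be accepted as the explanation. The primary PIIR analysis is unaffected.

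A reader might go further and infer that the exclusion biases a stroke comparison towards no difference. The documents do not support this, for two reasons. Section 10 specifies no stroke comparison. Nor is a direction established: if a fraction f of strokes is set aside in both arms, the counted rates are (1 − f)p₁ and (1 − f)p₂, and their ratio is still p₁/p₂. The absolute difference and the precision shrink, but the relative effect does not move. If f differs by arm, the distortion could go either way.

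The conclusion assumes only that sites apply the definition as written. It is worth acting on because the remedy is cheap and uses images already collected.

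**What to change.** 1. In Appendix III, define stroke for safety reporting as any new ischaemic or haemorrhagic stroke, or new infarct on CT, after the first study infusion, whatever the presumed cause.
2. Record presumed cause (vasospasm, procedure, drug or haemodynamic, aSAH, mixed, other) in a separate REDCap field. Name who assigns it, preferably someone blinded to arm.
3. Take new infarcts from a blinded core-lab read of the CTs already uploaded, with the pre-treatment scan as reference.
4. In section 10, tabulate the all-cause count by arm, with the cause split as supportive.
5. Send that count to the DSMB without the relatedness filter. Changing the definition alone would not remove that filter.

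The cost is one definition, one field, one table and an infarct item on the core-lab form. The reported stroke rate will be higher and will include disease-related events in every arm.

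Follow-up CTs will be incomplete, since section 6 allows contact by phone or email with mRS and NIHSS as the minimum. If CT loss matched the up to 20% loss that section 10 expects for mRS, 0.20 × 110 = 22 subjects per arm could lack one at full enrolment. The table should therefore give the number with a CT at each time point.

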1. NICARDIPINE

ADVERSE EVENTS:

Body as a Whole: headache, fever, neck pain Cardiovascular: hypertension, tachycardia, angina pectoris, atrioventricular block, ST segment depression, inverted T wave, deep vein thrombophlebitis Digestive: nausea, vomiting, dyspepsia Hemic and Lymphatic: thrombocytopenia Metabolic and Nutritional: hypophosphatemia, peripheral edema Nervous: confusion, hypertonia Respiratory: respiratory disorder Special Senses: conjunctivitis, ear disorder, tinnitus Urogenital: urinary frequency Sinus node dysfunction and myocardial infarction, which may be due to disease progression, have been seen in patients on chronic therapy with orally administered nicardipine.

OVERDOSAGE:

Several overdosages with orally administered nicardipine have been reported, IA overdoses are not known as yet.

One adult patient allegedly ingested 600 mg of nicardipine [standard (immediate-release) capsules], and another patient, 2160 mg of the sustained-release formulation of nicardipine.

Symptoms included marked hypotension, bradycardia, palpitations, flushing, drowsiness, confusion and slurred speech. All symptoms resolved without sequelae.

An over dosage occurred in a one-year-old child who ingested half of the powder in a 30 mg nicardipine standard capsule. The child remained asymptomatic.

Based on results obtained in laboratory animals, lethal overdose may cause systemic hypotension, bradycardia (following initial tachycardia) and progressive atrioventricular conduction block.

Reversible hepatic function abnormalities and sporadic focal hepatic necrosis were noted in some animal species receiving very large doses of nicardipine.

For treatment of overdosage, implement standard measures including monitoring of cardiac and respiratory functions. Position the patient so as to avoid cerebral anoxia. Use vasopressors for patients exhibiting profound hypotension.

